7.5. Preparation/Handling/Storage/Accountability

The investigator or his or her designee is responsible for the following:

- confirming appropriate temperature conditions have been maintained during transit for all study treatment received and any discrepancies are reported and resolved before use of the study treatment.
- ensuring that only participants enrolled in the study may receive study treatment and only authorized site staff may supply or administer study treatment. All study treatments must be stored in a secure, environmentally controlled, and monitored (manual or automated) area in accordance with the labeled storage conditions with access limited to the investigator and authorized site staff.
- the investigator, institution, or the head of the medical institution (where applicable) is responsible for study treatment accountability, reconciliation, and record maintenance (such as receipt, reconciliation and final disposition records).

The study site must store the study drug in a locked and secure environment. Please refer to the study drug label for specific storage conditions. Patients will receive insulated bags with cooling gel packs for use in transporting the study drug carton from the site to home.

Study site staff must regularly assess whether the patient is correctly administering the assigned study drug and storing the study drug according to the provided instructions.

7.6. Treatment Compliance

Study drug compliance will be determined by the following:

- Study drug administration data will be recorded by the patient and reviewed by the investigator at each study visit.
- The patients will be instructed to return any unused study drug and/or empty cartons at the next visit to the study site for the purpose of performing drug accountability.

In the 3 tirzepatide treatment groups, as well as the placebo group, treatment compliance for each visit interval is defined as taking at least 75% of the required doses of study drug. Patients will be considered to be noncompliant with their insulin glargine treatment if they miss their daily dose of insulin glargine for more than 7 consecutive days or for more than 7 days within a month (that is, a patient is considered to be compliant if they are $\geq 75\%$ compliant with their required

insulin glargine therapy). Similarly, a patient will be considered noncompliant if he or she is judged by the investigator to have intentionally or repeatedly taken more than the prescribed amount of medication.

In addition to the assessment of a patient's compliance with the study drug administration, other aspects of compliance with the study treatments will be assessed at each visit based on the patient's adherence to the visit schedule, completion of study diaries, the results of home BG monitoring, and any other parameters the investigator considers necessary.

Patients considered not to be compliant with their medication and/or the study procedures will receive additional training and instruction, as required, and will be reminded of the importance of complying with the protocol.

7.7. Concomitant Therapy

Patients will be permitted to use concomitant medications that they require during the study, except certain medications that may interfere with the assessment of efficacy and safety characteristics of the study treatments.

Investigative site staff will inform patients that they must consult with the investigator or a designated site staff member upon being prescribed any new medications during the study. This may not be possible when initiated for treatment of medical emergencies, in which case, the patient will inform the investigator or a designated site staff member as soon as possible. Any additional medication initiated during the course of the study (including OTC drugs, such as paracetamol or aspirin) must be documented, and the name of the drug and the date(s) of administration must be recorded on the "Concomitant Medications" section of the eCRF.

Antihyperglycemic medications other than study drugs are not allowed at any time during the study except as allowed for those patients who require permanent discontinuation of study drug, but remain in the study; rescue therapy after randomization due to severe, persistent hyperglycemia; or during the safety follow-up period. Glucagon-like peptide-1 receptor agonists, DPP-4 inhibitors, pramlintide, and other basal insulins are prohibited medications and are not allowed as rescue therapies.

All nonstudy medications will be recorded on the eCRF at all visits.

Nonstudy medications taken by patients who are screened, but not randomized will not be reported to Lilly unless an SAE or AE occurs that the investigator believes may have been caused by a study procedure.

7.7.1. Management of Patients with Gastrointestinal Symptoms

In the Phase 2 program, the most commonly reported treatment-emergent AEs (TEAEs) for patients receiving tirzepatide were nausea, vomiting, and diarrhea.

The tirzepatide dose escalation scheme has been designed to minimize the development of intolerable GI symptoms. The escalation period is considered to be 24 weeks, which allows

20 weeks to escalate to 15 mg and additional 4 weeks to reach steady state. During the dose escalation period, every effort should be made by the investigator to escalate and maintain patients on the corresponding study drug dosage.

To mitigate GI symptoms and manage patients with intolerable GI AEs during the escalation period (Weeks 0 to 24), the investigator should:

- Advise patients to eat smaller meals, for example, splitting 3 daily meals into 4 or more smaller meals, and to stop eating when they feel full.
- Prescribe symptomatic medication (for example, anti-emetic or antidiarrheal medication) per local country availability and individual patient needs. Use of symptomatic medication should be captured as concomitant medication in the eCRF.
- Temporarily interrupt tirzepatide (omit 1 dose, the patient will take 3 of 4 doses at that
 dose level). After the interruption, restart at the same dose with the patient taking
 medication to alleviate their GI symptoms. The data related to temporary interruption of
 study treatment should be documented in source documents and entered on the eCRF.
- If intolerable GI symptoms or events persist despite the above measures, the investigator
 may decide to discontinue study drugs. De-escalation of study drugs will not be allowed.
 Patients who stop the study drug permanently will receive another glucose-lowering
 intervention (Section 8.1.1) and will continue participating in the study according to the
 protocol to collect all planned efficacy and safety measurements. The new
 glucose-lowering intervention will be recorded on the eCRF specified for collecting
 antihyperglycemic medications.

In the event of intolerable persistent GI symptoms that occur after the escalation period (Week 24), the investigator should take the above measures to keep the patient on study treatment before stopping the study drug permanently and initiate another glucose-lowering intervention.

7.8. Treatment after the End of the Study

Study completion will occur after all patients complete the follow-up visit. Investigators will continue to follow Schedule of Activities (Section 2) for all patients until notified by Lilly that study completion has occurred.

Tirzepatide will not be made available after conclusion of the study to patients.

8. Discontinuation Criteria

8.1. Discontinuation from Study Treatment

8.1.1. Permanent Discontinuation from Study Treatment

Possible reasons leading to permanent discontinuation of investigational product:

Patient Decision

- o the patient requests to discontinue investigational product.
- **Discontinuation due to a hepatic event or liver test abnormality.** Patients who are discontinued from investigational product due to a hepatic event or liver test abnormality should have additional hepatic safety data collected via electronic case report form.

Discontinuation of the investigational product for abnormal liver tests **should be** considered by the investigator when a patient meets one of the following conditions after consultation with the Lilly designated medical monitor:

- o ALT or aspartate aminotransferase (AST) >8X ULN
- o ALT or AST >5X ULN for more than 2 weeks
- ALT or AST >3X ULN and total bilirubin level (TBL) >2X ULN or international normalized ratio (INR) >1.5
- o ALT or AST >3X ULN with the appearance of fatigue, nausea, vomiting, right upper-quadrant pain or tenderness, fever, rash, and/or eosinophilia (>5%)
- o alkaline phosphatase (ALP) >3X ULN
- o ALP >2.5X ULN and TBL >2X ULN
- o ALP >2.5X ULN with the appearance of fatigue, nausea, vomiting, right quadrant pain or tenderness, fever, rash, and/or eosinophilia (>5%)

In addition, patients will be discontinued from the investigational product in the following circumstances:

- If a patient is inadvertently enrolled and it is determined that continued treatment with study drug would not be medically appropriate
- Acute or chronic pancreatitis
- If a patient is diagnosed with MTC after randomization, or has postrandomization calcitonin value ≥35 ng/L that has increased at least 50% over baseline
- If a patient is diagnosed with an active or untreated malignancy (other than basal or squamous cell skin cancer, in situ carcinomas of the cervix, or in situ prostate cancer) after randomization
- Any significant study drug-related hypersensitivity reaction

- Any other TEAE, SAE, or clinically significant laboratory value for which the investigator believes that permanent study drug discontinuation is the appropriate measure to be taken
- · If female patient becomes pregnant
- If a patient is diagnosed with T1DM

Patients who stop the study drug permanently will receive another glucose-lowering intervention and will continue participating in the trial according to the protocol to collect all planned efficacy and safety measurements.

Patients discontinuing from the investigational product prematurely for any reason should complete adverse event and other follow-up procedures per Section 2 (Schedule of Activities), Section 9.2 (Adverse Events), and Section 9.4 (Safety) of this protocol.

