8.1.2. Temporary Discontinuation from Study Treatment

In certain situations after randomization, the investigator may need to temporarily interrupt study drug. Every effort should be made by the investigator to maintain patients on study drug and to restart study drug after any temporary interruption, as soon as it is safe to do so.

- If the number of doses missed is ≤2, the treatment can be restarted at the same dose, if the drug was well tolerated prior to discontinuation.
- If the number of missed doses is ≥3, then the IWRS will dispense 5 mg/matched placebo irrespective of the dose the patient was receiving before the interruption and subsequently escalated as required by protocol.

If study drug interruption is due to an AE, the event is to be documented and followed according to the procedures in Section 9.2 of this protocol. If the study drug interruption is due to intolerable persistent GI AE (for example, nausea, vomiting, or diarrhea), the patients should be treated as suggested in Section 7.7.1.

The data related to temporary interruption of study treatment will be documented in source documents and entered on the eCRF.

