9.2.2.4. Thyroid Malignancies and C-Cell Hyperplasia

Individuals with personal or family history of MTC and/or multiple endocrine neoplasia type 2 (MEN-2) will be excluded from the study. The assessment of thyroid safety during the study will include reporting of any case of thyroid malignancy including MTC and papillary carcinoma

and measurements of calcitonin. This data will be captured in specific eCRFs. The purpose of calcitonin measurements is to assess the potential of tirzepatide to affect thyroid C-cell function, which may indicate development of C-cell hyperplasia and neoplasms. Tirzepatide should be discontinued (after first confirming the value) if postrandomization calcitonin value is ≥35 ng/L and has increased at least 50% over baseline. A consultation with a thyroid specialist (if not available, an endocrinologist) should be obtained.

If the increased calcitonin value (≥35 ng/L and increases by ≥50% compared with baseline) is observed in a patient who has administered a medication that is known to increase serum calcitonin, this medication should be stopped and calcitonin levels should be measured after an appropriate washout period. If the confirmed calcitonin value is <35 ng/L, tirzepatide should be restarted when it is safe to do so.

- 9.2.2.5. Major Adverse Cardiovascular Events Deaths and nonfatal CV AEs will be adjudicated by a committee of physicians external to Lilly with cardiology expertise. The nonfatal CV AEs to be adjudicated include the following:
 - myocardial infarction,
 - hospitalization for unstable angina,
 - hospitalization for heart failure,
 - coronary interventions (such as coronary artery bypass graft or percutaneous coronary intervention), and
 - cerebrovascular events, including cerebrovascular accident (stroke) and transient ischemic attack.

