6.1. Populations for Analyses

For purposes of analysis, [Table GPGI.6.1](#) defines analysis populations/data sets.

Table GPGI.6.1. Analysis Populations/Data Sets

Population/Data Set	Description
Screened population	All participants who sign informed consent
Randomized population	All patients who are randomly assigned a treatment arm
Modified intention-to-treat (mITT) population	All randomly assigned participants who are exposed to at least 1 dose of study drug. In the event of a treatment error, participants will be analyzed according to the treatment they were randomized.
Efficacy analysis set (EAS)	Data obtained during Study Period II from the mITT population, excluding patients discontinuing study drug due to inadvertent enrollment and data after initiating rescue antihyperglycemic medication or early discontinuation of study drug (last dose date + 7 days).
Full analysis set (FAS)	All available data obtained during Study Period II from the mITT population, regardless of adherence to study drug or initiation of rescue antihyperglycemic medication. Patients who discontinued study drug due to inadvertent enrollment will be excluded.
Safety analysis set (SS)	All available data obtained during Study Periods II and III from the mITT population, regardless of adherence to study drug or initiation of new antihyperglycemic medication.

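### The calcitonin stopping rule in Protocol 8.1.1 is permanent and unqualified, while 9.2.2.4 directs a restart for some patients who meet the same thresholds

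*Protocol*

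**What the plan says.** Protocol 8.1.1 sits under the heading on permanent discontinuation. After the liver criteria, which the investigator only has to consider, it turns to a mandatory list: "patients will be discontinued from the investigational product in the following circumstances". One entry combines a diagnosis of medullary thyroid carcinoma with a "postrandomization calcitonin value ≥35 ng/L that has increased at least 50% over baseline". The entry mentions neither confirmation nor other medications, and it does not refer to 9.2.2.4.

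Protocol 9.2.2.4 covers the same finding with the same two thresholds. It asks for confirmation before any stop: "Tirzepatide should be discontinued (after first confirming the value) if postrandomization calcitonin value is ≥35 ng/L", with the same 50% rise. It then treats separately the patient who has taken a medication known to raise serum calcitonin. For that patient, "this medication should be stopped and calcitonin levels should be measured after an appropriate washout period". The paragraph ends: "If the confirmed calcitonin value is <35 ng/L, tirzepatide should be restarted when it is safe to do so".

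The only pointer from 8.1.1 to Section 9.2 concerns follow-up procedures after study drug has been stopped. It does not qualify the trigger.

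**The concern.** A site with a calcitonin result above the threshold has two operative instructions. Read alone, 8.1.1 ends study drug for good. Read alone, 9.2.2.4 returns study drug to a patient whose rise is explained by another medication and falls below 35 ng/L after washout. Two sites could therefore manage the same patient in opposite ways, each following the protocol. The site that follows 8.1.1 literally would permanently withdraw a patient whom the protocol, in its more detailed section, wants back on study drug.

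At stake are the remaining doses for that patient and, in the efficacy analysis set, the HbA1c values after the stop. That set excludes data beyond 7 days after the last dose once study drug has been discontinued early (SAP 6.1).

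**Working it through.** The plan states no figure on this point, so there is none to reproduce. The check compares the two rules case by case and then bounds the cost per patient.

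**Comparison.** Each patient has a first value of at least 35 ng/L that is at least 50% above baseline.

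| Case | 8.1.1 | 9.2.2.4 | Compatible? |
|---|---|---|---|
| Retest does not confirm | Silent on confirmation | No stop | Yes, if the site retests before acting |
| Confirmed, no other calcitonin-raising medication | Permanent stop | Stop | Yes |
| Other medication, still ≥35 ng/L after its washout | Permanent stop | No restart instruction | Yes |
| Other medication, <35 ng/L after its washout | Permanent stop | Restart when safe | No |

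Only the last row is a true conflict. No order of actions satisfies both a permanent stop and a restart.

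**Inputs for the cost** (Protocol Section 2, Schedule of Activities):
- Calcitonin is drawn after baseline, within the treatment period, at Weeks 12, 24 and 40.
- HbA1c is drawn after baseline at Weeks 4, 8, 12, 16, 20, 24 and 40, which is 7 values.
- Weekly doses are taken to fall in Weeks 0 to 39, which is 40 doses.

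**Upper bound against uninterrupted dosing.** If no dose is taken from the draw at Week w onward, doses forgone = 40 − w.
- Week 12: 40 − 12 = 28 of 40 (70%). HbA1c values after the draw: Weeks 16, 20, 24 and 40, so 4 of 7.
- Week 24: 40 − 24 = 16 of 40 (40%). HbA1c values after the draw: Week 40, so 1 of 7.
- Week 40: 0 doses and 0 values.

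These are ceilings, because a result arrives after the visit and a further dose may be taken first. The HbA1c counts apply to the efficacy analysis set. The full analysis set keeps data regardless of adherence, and 8.1.1 keeps stopped patients in the trial, so it loses none.

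**Against the course under 9.2.2.4.** In the conflicting case, 9.2.2.4 speaks of restarting, so study drug has been interrupted there too. If m doses are missed before restart, the dose loss due to 8.1.1 is (40 − w) − m. The documents give no washout length. Assuming m between 1 and 8, the loss is 27 down to 20 doses after the Week 12 draw, and 15 down to 8 after the Week 24 draw.

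Protocol 8.1.2 also sends a patient who misses 3 or more doses back to 5 mg (or matched placebo) to escalate again. In the 15 mg arm, assuming the usual steps of 2.5 mg every 4 weeks, the way from 5 to 15 mg is 4 × 4 = 16 weeks. A patient who misses 3 doses from Week 24 restarts at Week 27 and would reach 15 mg at Week 27 + 16 = 43, after the Week 40 endpoint. The restarted course is therefore well short of uninterrupted full dosing. The HbA1c loss in this branch can be no more than 4 or 1 values, and those values would come from an interrupted course.

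**The case against.** The strongest reply is that 8.1.1 is a summary list and 9.2.2 holds the detail. Pancreatitis is also a bare entry in 8.1.1, with its diagnostic criteria in 9.2.2.3. On that view the specific section governs. This has some force, and most sites would probably act that way. But 8.1.1 does not say that it is a summary, and other entries in it carry their own qualifiers, such as the two-week duration in one liver criterion. An unqualified mandatory entry can reasonably be read as unqualified.

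A second reply is that 8.1.1 nowhere says a single or unconfirmed value is enough. That stands. A reader might infer that 8.1.1 mandates a permanent stop on one unconfirmed result, but the text is silent on confirmation, and a site that retests first complies with both sections.

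A reader might also cite 8.1.2: "Every effort should be made by the investigator to maintain patients on study drug". That sentence concerns temporary interruptions. It does not limit a mandatory stop in 8.1.1 and adds no independent support.

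Finally, a reader might see the same conflict for hypersensitivity, since 8.1.1 lists "Any significant study drug-related hypersensitivity reaction" while 9.2.2.7 allows a restart. The documents do not support that. Section 9.2.2.7 deals with suspected reactions, permits restart only if safe, and itself provides for permanent discontinuation. The 8.1.1 rule continues to bind once a reaction is significant and drug-related.

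**Conclusion.** The inconsistency is real and narrow. For a patient whose calcitonin rise is explained by another medication and falls below 35 ng/L after washout, 8.1.1 requires a permanent stop and 9.2.2.4 directs a restart, with no cross-reference to settle it. The difference over confirmation is a lack of clarity that retesting resolves.

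Few patients should be affected. The documents give no event rate, and exclusion criterion [22] already removes patients with calcitonin of 35 ng/L or more at Visit 1, so the trigger requires a new crossing of that level. The per-patient bounds of 28 or 16 of 40 doses, and 4 or 1 of 7 efficacy analysis set values, assume dosing in Weeks 0 to 39, a stop at the draw itself, and uninterrupted dosing as the comparison. In the conflicting case the dose loss is smaller, because 9.2.2.4 also involves an interruption.

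A reader might infer a threat to the primary analysis. Nothing in the documents supports that: the full analysis set loses no data, and the size of any effect on the efficacy analysis set cannot be computed without a frequency.

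**What to change.** In the 8.1.1 entry, insert *confirmed* immediately before "postrandomization calcitonin value ≥35 ng/L that has increased at least 50% over baseline" and add after it: *except as described in Section 9.2.2.4*. This adopts the sponsor's own more detailed rule as the single instruction.

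The cost is a few words in one entry. No test, visit or judgement is added, because 9.2.2.4 already calls for the confirmatory value and the measurement after washout. Neither the SAP nor 9.2.2.7 needs to change for this point.

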8.1.2. Temporary Discontinuation from Study Treatment

In certain situations after randomization, the investigator may need to temporarily interrupt study drug. Every effort should be made by the investigator to maintain patients on study drug and to restart study drug after any temporary interruption, as soon as it is safe to do so.

- If the number of doses missed is ≤2, the treatment can be restarted at the same dose, if the drug was well tolerated prior to discontinuation.
- If the number of missed doses is ≥3, then the IWRS will dispense 5 mg/matched placebo irrespective of the dose the patient was receiving before the interruption and subsequently escalated as required by protocol.

If study drug interruption is due to an AE, the event is to be documented and followed according to the procedures in Section 9.2 of this protocol. If the study drug interruption is due to intolerable persistent GI AE (for example, nausea, vomiting, or diarrhea), the patients should be treated as suggested in Section 7.7.1.

The data related to temporary interruption of study treatment will be documented in source documents and entered on the eCRF.

8.1.3. Discontinuation of Inadvertently Enrolled Patients

If the sponsor or investigator identify a patient who did not meet enrollment criteria and was inadvertently enrolled, then the patient should be discontinued from study treatment unless there are extenuating circumstances that make it medically necessary for the patient to continue on study treatment. If the investigator and the sponsor CRP agree it is medically appropriate to continue, the investigator must obtain documented approval from the sponsor CRP to allow the inadvertently enrolled patient to continue in the study with or without treatment with investigational product. Safety follow up is as outlined in Section 2 (Schedule of Activities), Section 9.2 (Adverse Events), and Section 9.4 (Safety) of the protocol.

